APPENDIX B: Definitions for Adverse Event Reporting.....	33
APPENDIX C: Reporting Timelines.....	35
APPENDIX D: Study-Specific DSM Tables.....	37
APPENDIX E: Patient Reported Experience Measures (PREM) Form.....	38

PROTOCOL SUMMARY

Title:	A Novel Pilot Study of Online Proton Adaptive RadioTherapY (PARTy) Utilizing Computed Tomography On Rails
Study Description:	This pilot study aims to evaluate the feasibility of daily online adaptive planning for patients undergoing proton radiation therapy.
Objectives:	
Primary Objective: To assess the feasibility of online proton adaptive radiotherapy based on successful deliver of more than 70% of attempted fractions where treatment adaptation is indicated.
 
Secondary Objective: 1. To assess the safety of online proton adaptive radiotherapy.
 
Exploratory Objectives: 1. To assess patient tolerability and satisfaction with online proton adaptive radiotherapy process. 2. To assess dosimetric differences for target coverage and organ at risk (OAR) sparing between adaptive and non-adaptive proton therapy.

Endpoints:	
Primary Endpoint: Successful completion of online adaptive proton radiotherapy workflow through treatment delivery in at least 70% of planned adaptive fractions.
 
Success will be defined as PARTy plan creation and delivery of the fraction using the study workflow in one on-table attempt. Unsuccessful planning and workflow delivery will be defined as multiple attempts of the PARTy workflow for one treatment fraction without treatment delivery such that the study workflow is abandoned.
 
Secondary Endpoint: 1. Grade 2+ radiation-related toxicity at 3 months as measured by CTCAE v5.0
 
Exploratory Endpoints: 1. Patient reported experience measures (PREMs). 2. Dosimetry evaluation and comparison to non-adapted proton pre-plan.

Study Population:	The study plans to enroll 10 evaluable adult patients with any solid tumor (excluding small cell histology).

Phase:	Not Applicable
Description of Sites / Facilities Enrolling:	Patients will be treated at a single facility, at the S. Lee Kling Proton Therapy Center, as the technology required for this study is confined to this center.
Description of Study Intervention:	Patients planning to receive standard of care proton therapy will be consented to the study. After study enrollment, at time of each daily or every other day fraction, patients will undergo online evaluation for proton replanning based on prespecified dosimetric objectives of improving tumor coverage and/or normal organ at risk sparing.
Study Duration:	12 months accrual + 3.5 months for patient treatment and follow-up + 3 months analysis = 18.5 months
Participant Duration:	1 to 2 weeks of treatment + 3 months follow-up = 3.5 months

SCHEMA

SCHEDULE OF ACTIVITIES

Screening assessments should occur within 4 weeks prior to the start of SBRT unless otherwise noted. The window for the 3 mos post-Tx visit is +/-4 weeks.

Daily SBRT Schedule							
	Screening	D1	D2	D3	D4	D5	3 mos post-Tx
Informed consent	X						
Medical history	X						
H&P	X						X
Volumetric imaging ¹	X						
Pregnancy test ²	X						
Diagnostic scan based preplan ³	X						
Adaptive proton SBRT		X	X	X	X	X	
Patient Reported Experience Measures						X ⁴	
Adverse events assessment		X-----X					

¹ CT, MRI, or PET are acceptable as per routine clinical evaluation at the discretion of the treating physician.

² Women of childbearing potential only; within 14 days prior to the start of treatment.

³ Initial radiation treatment plan based on standard CT simulation.

⁴ Questionnaire of patients' experience with adaptive workflow, given at the end of the last treatment (window +7 days).

Every Other Day SBRT Schedule ⁵							
	Screening	D1	D3	D5	D7	D9	3 mos post-Tx
Informed consent	X						
Medical history	X						
H&P	X						X
Volumetric imaging ¹	X						
Pregnancy test ²	X						
Diagnostic scan based preplan ³	X						
Adaptive proton SBRT		X	X	X	X	X	
Patient Reported Experience Measures						X ⁴	
Adverse events assessment		X-----X					

¹ CT, MRI, or PET are acceptable as per routine clinical evaluation at the discretion of the treating physician.

² Women of childbearing potential only; within 14 days prior to the start of treatment.

³ Initial radiation treatment plan based on standard CT simulation.

⁴ Questionnaire of patients' experience with adaptive workflow, given at the end of the last treatment.

⁵ RT will not be administered on a weekend; a 2 day break in between fractions due to scheduling is acceptable (window +7 days).

1.0 BACKGROUND AND RATIONALE

1.1 Rationale for Proton Radiotherapy

While photon-based linear accelerators remain the primary method for modern radiation therapy, proton radiotherapy has emerged as an alternative approach with unique dose delivery characteristics.

Conventional photon radiotherapy is delivered using a linear accelerator (LINAC) that generate high energy X-rays or photons. A photon radiation beam deposits most of its energy as it enters the body and continues to release energy as it passes through tissue resulting in both entrance and exit radiation doses. The introduction of intensity modulation and inverse treatment planning has further minimized radiation exposure to surrounding healthy tissues by enabling modulation of the beam into separate beamlets to improve conformality.¹ Nonetheless, in most instances, there remains a residual low-dose radiation exposure to normal tissues.

Compared to photon radiation, proton therapy offers an advantage of minimizing radiation exposure to critical Organs at Risk (OARs). This is primarily attributed to the unique dose distribution of protons, allowing the dose to deposit most of their energy within the targeted volume and subsequently stop, limiting further radiation dose to healthy tissues beyond the target. As a result, proton therapy may offer superior sparing of OARs, reducing the potential for unnecessary radiation dosing to surrounding healthy organs.

This feature makes proton therapy particularly advantageous for cancer cases where minimizing radiation to critical OARs or lowering total integrated dose is paramount, such as in pediatric cancers and in reirradiation cases. As planning and access to proton therapy have become more widespread, its clinical benefit has been demonstrated to more diverse cancer sites, including cancers of the head and neck, esophagus, breast, and lung.²⁻⁵

1.2 Online Adaptive Radiation Therapy

Another potential method for further minimizing unnecessary radiation dose is through adaptive radiotherapy. Adaption in radiation therapy is the process of modifying a patient's treatment plan during the course of fractionated radiotherapy treatment to account for changes in patient anatomy, tumor size, or changes in setup in order to ensure the treatment plan remains effective and safe for the patient.

Adaptation for radiotherapy can occur either offline or online. Offline adaptive radiation therapy is a common practice for various cancer types, both in proton and photon therapy.⁶ Typically, offline adaptation involves re-evaluation of treatment plans based on imaging and clinical factors during treatment. Offline adaptation is typically completed between treatment sessions with a revised treatment plan used for future sessions. Internally, we have been using offline adaptation in patients treated with proton therapy.⁷

Conversely, online adaptation occurs just before each treatment fraction is delivered, allowing for more immediate adjustments. Online adaptation is particularly advantageous

for abdominal malignancies as it enables precise alignment of the radiation plan with the target and allows for plan modifications based on daily bowel motion, which offers significant dosimetric benefits for patients with cancerous lesions in the abdominal region. This is achieved through daily high quality MRI or cone beam CT scan just before their daily treatment session. The original treatment plan contours, created during simulation, are then superimposed onto the most recent scans of the day. If any necessary adjustments to the target and organs at risk (OARs) are identified, they are incorporated into a modified plan, which is subsequently administered.

There have been numerous studies that affirm the effectiveness of online adaptive radiotherapy using CT and MRI guidance.⁷⁻⁹ These studies have demonstrated good disease control with acceptable or improved toxicity profiles. These studies included patients treated for malignancies in the abdominal region for which adaptive radiation is particularly attractive due to the substantial changes in position between treatments for luminal gastrointestinal (GI) structures.^{10,11} The integration of CT and MRI guidance for online adaptation has enabled the delivery of ablative radiation doses to abdominal malignancies by accounting for daily positional changes of target and nearby critical OARS. Online adaptation has also proven effective in the treatment of thoracic malignancies and breast cancers, allowing for tailored and precise radiation therapy to optimize treatment outcomes.

1.3 Limitations of Proton Dosimetry and Rationale for Online Adaptive Proton SBRT

Although proton therapy offers dosimetric advantage of highly conformal radiation and finite proton beam range, accounting for uncertainties in treatment delivery remains a significant challenge. Plan robustness for protons accounts for range uncertainty from poor CT calculation and insufficient heterogeneity correction, changes in patient anatomy, proton energy variations and relative biological effectiveness dose assumptions.¹² The result of these uncertainties can compound and lead to overdosing healthy tissue and under-treating the intended target.

In the context of treatment planning, margins are a common approach to account for uncertainties and increase the likelihood of adequately covering the target volume. However, applying margins in proton therapy presents challenges, primarily due to site-specific range uncertainties and range uncertainty variations across specific beam angles.

Another strategy to address uncertainties in proton dosimetry is robust optimization, which integrates uncertainty models into the treatment plan optimization process. This approach aims to strike a balance between ensuring target volume coverage while sparing OARs. However, establishing a precise and reliable uncertainty model to predict anatomical variations in proton treatment planning can be particularly challenging. Consequently, robust optimization alone may not always be sufficient to consistently deliver a dependable and accurate treatment plan.

Due to such challenges, there is an unmet need to explore online adaptation methods in proton radiotherapy. Even minor daily uncertainties can lead to significant dose deviations due to dose conformality and finite range of proton beams potentially resulting in inadequate target volume coverage and overdosing OARs.

The implementation of daily online adaptation and delivery of daily optimized treatment plans provides a means to combine the specific dosimetric advantages of proton therapy with adaptive radiotherapy. This approach enables a more precise and effective radiation dose to the tumor while effectively accommodating daily uncertainties. Consequently, it minimizes radiation exposure to healthy tissues, optimizing the therapeutic impact while concurrently reducing the potential for radiation-induced toxicity to nearby OARs.

1.4 Preliminary Studies

The following is a proposed workflow for online adaptive proton therapy. This workflow draws upon our institutional expertise in MR-guided and CT-guided online adaptive radiotherapy.

[figure not shown]

Fig. 1 Proposed online adaptive proton radiotherapy workflow

[figure not shown]
The process initiates with the daily acquisition of CT images using our in-room CT-on-rails system. These images are imported into RayStation, where adjustments to contours and volumes are made by our dosimetry team with an overseeing physician. A physician is present at the machine to review, approve these contours and adjust contours as needed. Subsequently, the plan undergoes reoptimization and passes through an in-house physics quality assurance (QA) algorithm. The physician then conducts a final review of the adapted plan and grants approval. A formal treatment plan is generated and loaded onto the

treatment machine. To ensure no significant setup changes have occurred during the adaptation process, an additional CT image is acquired.

Investigation into the technical and logistical feasibility of the proposed workflow has been performed through an in-silico analysis. This study utilized patients who underwent proton therapy for rectal cancer recurrence as part of the IMPARC clinical trial (NCT04827732). Specifically, eight patients with rectal or other pelvic malignancies, previously treated on a proton dose escalation trial over five fractions, routinely received daily CT-on-rails imaging prior to each fraction.

We determined that the average time required to complete the online adaptive process ranged from 33 to 45 minutes.¹³ In typical proton planning, robust optimization and evaluation are employed, incorporating a 5mm setup uncertainty and a 3% proton range uncertainty for non-adaptive proton plans. However, for adaptive plans, we have the flexibility to eliminate setup uncertainty and optimize and evaluate with only a 3% proton range uncertainty, thereby reducing the dose to organs at risk (OAR) (figure 2).

5mm, 3%

0mm, 3%

[figure not shown]

Fig 2. 5mm setup uncertainty and a 3% proton range uncertainty for non-adaptive plans vs 0mm setup uncertainty and 3% proton range uncertainty for adaptive plans

1.5 Study Rationale

Building upon our initial preliminary study and drawing from our institutional experience in online adaptation, as well as our capability to acquire high-quality CT scans while the patient is on the treatment table, the focus of this study is to demonstrate the feasibility of implementing this workflow for clinical use.

By using an online adaptation approach, we will combine the advantages of proton dosimetry while addressing the dosimetric challenges posed by proton therapy due to daily anatomical and tissue density variations. Establishing this workflow has the potential to enhance the effectiveness of proton therapy while simultaneously minimizing the adverse effects and radiation-related toxicity.

This study's objective is to demonstrate clinical feasibility and safety of the Proton Adaptive RadioTherapy (PARTy) workflow for patients who are suitable candidates for proton therapy and who could benefit from online adaptation based on anatomical considerations. We aim to demonstrate successful completion of the PARTy workflow in at least 70% of adaptive treatment fractions throughout the treatment delivery process.

1.6 Overall Design

This is a pilot study evaluating the feasibility of implementing an online adaptive workflow for patients undergoing treatment with proton radiotherapy.

1.6.1 Scientific Rationale for Study Design

The aim of this pilot study is to evaluate the feasibility of implementing an online adaptive workflow for patients receiving proton therapy in order to provide data for a larger evaluation of online adaptive proton therapy.

1.7 Risk/Benefit Assessment

1.7.1 Known Potential Risks

The medical risks from participating in this study revolve around exposure to proton radiation and increased time required per treatment to allow for day of plan adaptation. Treatment options for patients enrolled in this study include irradiating with online adaptive stereotactic body radiation treatments (SBRT) over 5 days every day or every other day to a dose of 25-50 Gy. All patients undergoing five fractions or fewer fractions with protons would be evaluated for eligibility for this study during a twice weekly proton triage meeting. Patients enrolled in this study would be deemed appropriate for non-adaptive proton SBRT by the treating radiation oncologist.

Adaptive radiation planning enables improved target coverage by accounting for daily changes in anatomy. This results in a higher integrated dose to the tumor, which has the potential of increased radiation toxicity. However, similar studies of photon based radiation adapted planning have shown this approach to be safe, with comparable levels of acute toxicity seen in both adapted and non-adapted conventional plans.

With online adaptation radiation treatment plans, the time a patient spends lying on treatment table may be extended (45-90 minutes) compared to non-adapted conventional plans (20-30 minutes).

1.7.2 Known Potential Benefits

Online adaptation has the potential to modify the treatment plan based on set up and anatomical changes that may occur between initial simulation and days of treatment. Online adaptation can enable improved target coverage and ability for better OAR sparing leading to more precise treatment delivery with reduced toxicity.

1.7.3 Assessment of Potential Risks and Benefits

Given the above potential risks and benefits, we believe that the benefits of performing online adaptation for patients receiving proton therapy outweigh the risks.

2.0 OBJECTIVES AND ENDPOINTS

Objectives	Endpoints
Primary	
To assess the feasibility of online proton adaptive radiotherapy based on successful delivery of more than 70% of attempted fractions where treatment adaptation is indicated.	
Successful completion of online adaptive proton radiotherapy workflow through treatment delivery in at least 70% of planned adaptive fractions.
 
Success will be defined as PARTy plan creation and delivery of the fraction using the study workflow in one on-table attempt. Unsuccessful planning and workflow delivery will be defined as multiple attempts of the PARTy workflow for one treatment fraction without treatment delivery such that the study workflow is abandoned.

Secondary	
1. To assess the safety of online proton adaptive radiotherapy.	1. Grade 2+ radiation-related toxicity at 3 months as measured by CTCAE v5.0.
Exploratory	

 To assess patient tolerability and satisfaction with online proton adaptive radiotherapy process. To assess dosimetric differences for target coverage and organ at risk (OAR) sparing between adaptive and non-adaptive proton therapy. 	
 Patient reported experience measures (PREMs). Dosimetry evaluation and comparison to non-adapted pre-plan.

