5.2 Definitions of Evaluability

Endpoint	In order to be evaluable for this endpoint, a patient must...
Primary: feasibility of online proton adaptive radiotherapy	Have received at least one fraction of SBRT.
Secondary: G2+ toxicity at 3 months	
Exploratory: dosimetry evaluation and comparison to non-adaptive workflow	
Exploratory: PREMs	Have received at least one fraction of SBRT and completed PREMs.

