5.5 Duration of Therapy

If at any time the constraints of this protocol are considered to be detrimental to the patient's health and/or the patient no longer wishes to continue protocol therapy, the protocol therapy should be discontinued and the reason(s) for discontinuation documented in the case report forms.

In the absence of treatment delays due to adverse events, treatment may continue for a total of 5 fractions of SBRT or until one of the following criteria applies:

- Documented and confirmed disease progression
- Intercurrent illness that prevents further administration of treatment
- Death
- Unacceptable adverse event(s)
- General or specific changes in the patient's condition render the patient unacceptable for further treatment in the judgment of the investigator
- Suspected pregnancy
- Serious non-compliance with the study protocol
- Lost to follow-up
- Patient decides to withdraw from the study
- The Siteman Cancer Center decides to close the study

Patients who prematurely discontinue treatment for any reason will still be followed as indicated in the study calendar.

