10.0 Measurement of Effect

Because this study is a feasibility study and patients enrolled in this study will have distinct disease sites and heterogeneous treatment plans, measurement of treatment response will be at the discretion of treating radiation oncologist.

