11.0 STATISTICAL CONSIDERATIONS

11.1 Definition of Primary Endpoint

Feasibility: Feasibility will be defined as successful completion of online adaptive proton radiotherapy workflow through treatment delivery in at least 70% of planned adaptive fractions..

Success will be defined as PARTy plan creation and delivery of the fraction using the study workflow in one on-table attempt. Unsuccessful planning and workflow delivery will be defined as multiple attempts of the PARTy workflow for one treatment fraction without treatment delivery such that the study workflow is abandoned.

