11.4 Statistical Analysis Plan

The primary objective is to demonstrate that online proton adaptive radiotherapy is feasible by confirming that adaptive treatment can be delivered in more than 70% of treatment fractions where treatment adaptation is indicated.

Our principal objectives in this trial will be to determine the feasibility for online proton adaptive radiotherapy. If we can successfully deliver treatments for more than 70% of treatment fractions where treatment adaptation is indicated while maintaining the safety, then we will consider this study as having provided sufficient pilot data to support more widespread study of online proton adaptive radiotherapy. Historical controls reference 70% as the definition of feasibility, so we have utilized that for our primary endpoint. Basic descriptive statistics will be used to evaluate feasibility. The long-term goals will be to improve patient outcomes and care by improving target coverage and decreasing radiation toxicity.

Regarding toxicity, we will report descriptive statistics for acute toxicity at a three-month time point. Toxicity rates are anticipated to be identical or improved to those of other linear accelerator based SBRT treatments. Other than the online adaptation component of the treatment plan, patients will receive disease site specific standard-of-care dose and fractionation treatment plan. Therefore, further prospective toxicity assessments are not indicated. Given that no prior data exists for online adaptive proton radiotherapy, we will report descriptive statistics. Descriptive statistics will be calculated on all variables. Frequencies will be computed for all binary/categorical variables, and continuous variables will be summarized using medians, quartiles, and ranges. Patient satisfaction measured with PREMS will be evaluated using descriptive statistics. As a pilot study we will establish these baseline parameters.

For the dosimetry exploratory endpoints, non-parametric equivalents (Wilcoxon test) will be conducted to compare plan quality between simulated pre-plans and online adaptive plans. Further analysis may be conducted with ANCOVA to estimate how the baseline covariates associated simulated pre-plans and online adaptive plans. The ANCOVA will be presented with least square (LS) mean estimate. Two-sided 95% confidence intervals for the mean changes and p-values will also be reported.

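### The primary feasibility rate has conflicting denominators and no rule for planned fractions never started after a patient leaves the adaptive workflow, so it can be biased upward and cross 70%

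*Combined protocol and SAP*

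**What the plan says.** The primary rate is described in three ways.

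- **Objective** (section 2.0, repeated in the Protocol Summary and Appendix D): "successful delivery of more than 70% of attempted fractions where treatment adaptation is indicated".
- **Endpoint** (section 2.0, also in the Protocol Summary): "Successful completion of online adaptive proton radiotherapy workflow through treatment delivery in at least 70% of planned adaptive fractions". Section 11.1, the formal definition, uses the same denominator.
- **Go rule** (section 11.4): "adaptive treatment can be delivered in more than 70% of treatment fractions where treatment adaptation is indicated". If this is met while safety is maintained, the study is taken to support wider investigation.

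The threshold moves too: above 70% in the objective and in 11.4, 70% or above in the endpoint and in 11.1.

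A success is a plan created and delivered in a single on-table attempt. A failure is several attempts at one fraction that end without delivery, with the workflow abandoned (sections 2.0 and 11.1). To be evaluable for the primary endpoint a patient must "Have received at least one fraction of SBRT" (section 5.2).

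Section 5.5 allows early exit, on grounds of harm or by choice: if "the patient no longer wishes to continue protocol therapy, the protocol therapy should be discontinued", with the reason documented in the case report forms. Section 5.0 has the comparison of pre-plan and adapted plan repeated at every treatment.

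**The concern.** A fraction that is never started fits neither the success nor the failure definition. Whether it counts against feasibility therefore depends on the denominator, and the documents give three.

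With an attempted denominator, a patient who fails at fraction 1 and leaves the adaptive workflow contributes one failure, while a patient in whom it works contributes five successes. A patient who leaves because the procedure is not tolerated may contribute no failure at all. Section 1.7.1 puts table time at 45-90 minutes with adaptation against 20-30 minutes without, so intolerance is a foreseeable reason to leave.

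The wording in 11.4 does not clearly avoid this. Under section 5.1.6 the decision to adapt is made on the day, after the two plans are compared. For a patient who has left the workflow no adapted plan is made, so arguably no indication exists and the fraction can disappear there as well.

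At stake is the go decision in 11.4. Two analysts could each follow the protocol and reach opposite conclusions from the same data.

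**Working it through.** **Plan's own figure.** None to reproduce. Section 11.3 sets the sample size on clinical considerations, and the only stated criterion is the 70% line.

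**Inputs from the documents.** 10 evaluable patients (11.3) and 5 fractions each (5.1.1), so 10 × 5 = 50 planned fractions. At 50 fractions the two threshold wordings differ by one success: 35/50 = 70.0% satisfies *at least 70%*, but *more than 70%* needs 36.

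**Assumptions.** Adaptation is indicated at all 50 fractions. The number of patients who leave, and the correlation of success within patients, are not in the documents and are varied below.

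**Step 1: exit after a failure.** Let *k* patients fail at fraction *f* and leave, with every other attempted fraction successful.

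- Successes: S = 5(10 − k) + k(f − 1)
- Attempted: A = 5(10 − k) + kf
- Planned: 50

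| f | k | S/A (attempted) | S/50 (planned) |
|---|---|---|---|
| 1 | 3 | 35/38 = 92.1% | 70.0% |
| 1 | 4 | 30/34 = 88.2% | 60.0% |
| 1 | 6 | 20/26 = 76.9% | 40.0% |
| 1 | 7 | 15/22 = 68.2% | 30.0% |
| 2 | 4 | 34/38 = 89.5% | 68.0% |
| 3 | 4 | 38/42 = 90.5% | 76.0% |

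The conclusion reverses at k = 4 and 6 with f = 1, and at k = 4 with f = 2. It does not at k = 4 with f = 3 (both pass) or k = 7 with f = 1 (both fail). At k = 3 with f = 1 the planned rate sits on the line, so the answer depends on the threshold wording.

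**Step 2: exit for tolerability, with no failed attempt.** If 6 patients leave after two successful fractions, S = 5 × 4 + 2 × 6 = 32. The attempted rate is 32/32 = 100% and the planned rate 32/50 = 64%.

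**Step 3: is upward bias automatic?** It is not. 40,000 trials were simulated with 10 patients, 5 fractions, mean success 60% and beta-distributed patient-level probabilities. Every failure led to exit.

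| Intraclass correlation (ICC) | Mean attempted-only rate |
|---|---|
| 0 | 58% |
| 0.1 | 62% |
| 0.3 | 69% |
| 0.5 | 75% |

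With a common success probability the mean is not inflated. It rises as patients differ more, because those in whom the workflow does badly leave early and contribute few fractions.

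At ICC 0.3 the chance that the attempted-only rate exceeds 70% is about 14% if nobody leaves, 36% if half of failures lead to exit and 53% if all do. At ICC 0 it goes from about 5% with no exit to 12% with exit after every failure.

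**Step 4: what the planned rate measures.** At ICC 0.3 with exit after every failure, counting all remaining fractions as not delivered gives a mean of about 38%, against the underlying 60%. With exit after half of failures, the planned rate averages about 46% and the attempted-only rate about 66%.

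**The case against.** A reader might infer from the objective that the primary rate counts only attempted fractions and is therefore biased upward. The documents do not support that. The endpoint in 2.0 and the formal definition in 11.1 both say *planned*; *attempted* appears only in the objective wording. Nor is the direction of bias fixed, as step 3 shows.

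Exit is also less prominent in the plan than the examples suggest. No section removes a patient from adaptation after a failed fraction, and 5.0 expects the process at every treatment. Exit rests on the general discontinuation language of 5.5. Section 10.0 does say that "patients enrolled in this study will have distinct disease sites and heterogeneous treatment plans", but that explains why response is not standardised and gives no correlation for workflow success.

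Counting unstarted fractions as not delivered has its own cost. If the target is how often the workflow would succeed were all five fractions attempted, step 4 shows this rule can miss by more (about 38% against 60%) than the attempted-only rate does (69%). Finally, this is a 10-patient descriptive pilot without a hypothesis test.

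Most of this stands as a limit on size and certainty. It does not remove the gap. The word *planned* is in the endpoint, but *planned adaptive* is not defined and the rule that triggers wider study does not use it. Being expected to continue is not a counting rule for those who stop. Although the analysis is descriptive, 11.4 ties a decision to the rate.

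**Conclusion.** The point holds as a conflict of denominators with a missing counting rule. The attempted wording, and possibly that of 11.4, lets planned fractions drop out for reasons tied to the outcome, so the rate *can* be biased upward and *can* cross 70%. The clearest case is 30/34 = 88% against 30/50 = 60%, with 4 of 10 patients failing at fraction 1 and leaving. That rests on adaptation being indicated at all 50 fractions and no other failures.

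How likely this is cannot be derived from the documents. With exit after every failure and mean success of 60%, the average attempted-only rate runs from 58% to 75% over ICC 0 to 0.5. The tolerability example needs no assumption about that correlation, only that patients leave. The planned denominator is preferable because it is already in the formal endpoint and fits the question of whether the workflow can be carried through the planned course. It is not an unbiased estimate of per-attempt success.

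**What to change.** 1. Use the endpoint's *planned adaptive fractions* as the single denominator, with one threshold wording, in sections 2.0, 11.1 and 11.4 and Appendix D, and in the Protocol Summary, which repeats the text.
2. Define the term per fraction, including how a started fraction counts when the pre-plan is chosen because adaptation was not indicated. That is a separate question, but the definition has to answer it.
3. State that, for every patient who starts SBRT, planned fractions at which adaptation is not attempted because of an earlier workflow failure, intolerance or refusal count as not successfully delivered. Leave out only fractions missed for reasons unrelated to the workflow, such as disease progression or intercurrent illness.
4. Report the attempted-only rate as a sensitivity analysis, with the number of patients and fractions lost and the reasons.

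**Cost.** A few sentences of text. The reported rate may be clearly lower and becomes a measure of workflow success plus retention over the planned course; the report should say so. Some extra data may be needed: 5.5 requires a reason when protocol therapy is discontinued, but a patient who completes the course on the pre-plan has not clearly discontinued. The forms listed in section 8.0 show no per-fraction reason for non-adaptation, so one such field may have to be added.
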